#### 2.4 DESCRIPTION OF STUDY PROCEDURES

## 2.4.1 Echocardiogram

Transthoracic echocardiograms will be completed to assess RV function by measures such as TAPSE as well as to assess the Doppler waveform of the pulmonary artery. This is a noninvasive test.

## 2.4.2 Six Minute Walk Test (6MWT and Borg Scale)

The six-minute walk test (6MWT) will be conducted in accordance with local standard operating procedures. The 6MWT measures the distance an individual is able to walk over a total of six minutes on a hard, flat surface. The subject is allowed to self-pace and rest as needed as they traverse back and forth along a marked walkway. The test is used as a performance-based measure of functional exercise capacity. It evaluates the global and integrated responses of all the systems involved during exercise, including the pulmonary and cardiovascular systems, systemic circulation, peripheral circulation, blood, neuromuscular units, and muscle metabolism. The self-paced 6MWT assesses the submaximal level of functional capacity. Most subjects do not achieve maximal exercise capacity during the 6MWT; instead, they choose their own intensity of exercise and are allowed to stop and rest during the test. However, because most activities of daily living are performed at submaximal levels of exertion, the 6MWT may best reflect the functional exercise level for daily physical activities.

The Borg Scale is a method of rating perceived exertion during exercise and will be used while the subject performs a 6MWT.

#### 2.4.3 Accelerometer

Physical activity: The SenseWear Pro Armband Accelerometer (BodyMedia, Pittsburgh, PA and/or Actigraph, Pensacola, FL) multi-sensor device will be used to provide an objective measure of physical activity for about 7-10 days.

#### 2.4.4 Spirometry

Spirometry testing at baseline will consist of the Forced Vital Capacity (FVC) maneuver. A trained pulmonary function technician will administer the pulmonary function testing. The FVC is the maximal volume of air exhaled with a maximally forced effort from a maximal inspiration. The FVC maneuver will be performed using the Easy on-PC (NDD) with the subject in a seated position. Within the FVC maneuver, the maximal volume of air exhaled in the first second of a forced expiration (FEV1) will be obtained as well. The best of three efforts will be defined as the highest FEV1 and the highest FVC, each obtained on any of three efforts that meet the American Thoracic Society (ATS) guidelines for acceptability and repeatability criteria (with a maximum of eight attempts). The highest FEV1 and FVC will be selected regardless of whether they come from different spirometric maneuvers or from the same maneuver.

If the ratio of FEV1/FVC is less than 0.70, then salbutamol (albuterol) will be administered. After a gentle and incomplete expiration, a dose of 100  $\mu$  g of salbutamol (albuterol) is inhaled

in one breath to total lung capacity. The breath is inhaled for 10 seconds before the subject exhales. Four separate doses (total dose  $400\,\mu$  g) are delivered at approximately one minute intervals. Three additional, acceptable post-bronchodilator FVC manoeuver tests will be recorded 15 to 30 minutes after the last dose of salbutamol (albuterol) is inhaled.

## 2.4.5 Cardiopulmonary Exercise Testing (CPET) and Gas Exchange Measurements:

CPET will be performed using an electromagnetically braked cycle ergometer (Ergoline 800, SensorMedics) and the gas exchange measurements will be analyzed using the Viasys Vmax Encore metabolic cart system.

CPET at baseline will consist of an incremental exercise test (IET) and a constant work rate test for practice (CWRP). The CWRP test will determine the constant workrate (CWR) that will be used at baseline, Week 10, crossover, and EOT.

## Determining Workload (WL) and CWR at Baseline

- IET:The work rate will increase in a stepwise manner, using an individualized incremental WL (based on age, height, weight, and gender) to achieve a targeted duration of 4 to 12 minutes to volitional exhaustion. The incremental WL will be determined to the nearest multiple of 5 watts [69].
- CWRP: A resting period of at least 2 hours will be scheduled between exercise tests. The CWR is a set work rate that remains unchanged throughout the duration of the test. The CWRP will be performed around 70-75% of the maximal WL from the IET [70, 71]. Further adjustment in CWR will be based on the exercise endurance time (ET) of CWRP to optimize CWR at baseline, Week 10, crossover, and EOT\_to achieve a target duration of 4 to 12 minutes. ET will be measured from the start of loaded pedaling to volitional exhaustion and the WL has returned to unloaded pedaling. If a patient is unable to reach 4 minutes, the patient may be asked to return on a separate day to repeat the CWRP to adjust to a workload the patient can endure for at least 4 minutes. The second test will be optional.

## CPET for baseline, Week 10, crossover, and EOT

The CWR determined from CWRP will be used for baseline, Week 10, crossover, and EOT. ET will be measured from the start of loaded pedaling to volitional exhaustion and the WL has returned to unloaded pedaling. The endurance exercise challenge will be used to compare oral nitrite to placebo.

CPET will measure the integrated response of the pulmonary mechanics, gas exchange, cardio/pulmonary vascular, peripheral muscle systems, and the subject's perceived exertion. For each subject, isotime measurements of cardiopulmonary metabolic responses will be compared over the minimum ET of Week 10 and EOT. Data will be reported on an exercise test form.

A detailed description of the CPET procedures is provided by the CPET lab.

Emergency equipment including a defibrillator will be readily available.

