#### 2.6.2 Secondary Endpoints

Secondary endpoints:

- 1.The differences in 6MWT with Borg dyspnea scale assessments and pulse oxygen saturation measurements
- 2. RHC hemodynamics (right atrial pressure, pulmonary capillary wedge pressure, pulmonary artery pressures and resistance, pulmonary artery compliance, cardiac output, diastolic pressure gradients, and transpulmonary gradient)
- 3. Doppler-echocardiography
- 4. NT-proBNP plasma levels

- 5. NYHA functional classification changes
- 6. NO2 metabolites
- 7. Endurance exercise time (ET), changes in CPET measurements taken at isotime (oxygen consumption [VO2, L/min], minute ventilation [VE, L/min], ventilatory equivalent [VE/VO2], dead space to tidal volume ratio [Vd/Vt], Borg dyspnea and leg score, and changes in time constants for increases of Vt, respiratory rate [RR], VE, and heartrate).
- 8. Changes in fasting glucose and insulin sensitivity

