## 2.8 STATISTICAL ANALYSIS

#### 2.8.1 Sample Size and Power

**Sample size:** Prior study has indicated that oral nitrate reduces baseline mean PAP -7 (SD = 4) mm Hg vs. -3 (4) mmHg in placebo group. A sample size of 12 in each group provides 88%

power to detect this difference. This sample size will provide 80% power to detect -10 (6) vs. -5 (6) decrease in post-exercise mPAP in treatment and placebo group, respectively.

**Statistical analysis:** Pre-randomization characteristics of two groups will be presented using the median (interquartile range) or frequency tables at each study sequence. The difference of mPAP during submaximal exercise as compared between placebo and nitrite at 10 weeks (i.e. the week 10 RHC of placebo vs week 10 RHC of nitrite) using the parametric PK-cross analysis (i.e. an ANOVA which determines the sequence, period, carryover, and treatment effects). Post-exercise values of before and after crossover will be compared between two groups using similar approach. For secondary outcomes, we will compare the difference of baseline and follow-up value and compare these differences with a parametric test. Alternatively a nonparametric test will be used for these comparisons. For both primary and secondary outcomes, treatment effect in each sequence as well as mean (SD) total treatment effect and corresponding P values will be reported.

We will also test the effect of treatment on pre-exercise mPAP and secondary outcomes using mixed effect models. In all analysis, missing data will be imputed and sensitivity analysis with imputed data will be performed. All analyses will be performed by ITT approach.

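### Isotime is fixed by the Week 10 and EOT tests alone, but the isotime endpoint is to be analysed as change from baseline, so a baseline value will not exist for some patients

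*Combined protocol and SAP*

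**What the plan says.** Section 2.4.5 sets one constant work rate per patient, which "will be used for baseline, Week 10, crossover, and EOT". Each test is symptom-limited: "ET will be measured from the start of loaded pedaling to volitional exhaustion". The work rate is tuned "to achieve a target duration of 4 to 12 minutes". Isotime is then set patient by patient: "isotime measurements of cardiopulmonary metabolic responses will be compared over the minimum ET of Week 10 and EOT". The baseline and cross-over tests do not enter that minimum.

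Secondary endpoint 7 (synopsis and section 2.6.2) is "Endurance exercise time (ET), changes in CPET measurements taken at isotime", covering VO2, VE, VE/VO2, Vd/Vt and Borg scores. It does not name the test from which change is measured.

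Section 2.8.1 gives the primary endpoint a direct comparison of the two on-treatment catheterizations. It treats the rest differently: "For secondary outcomes, we will compare the difference of baseline and follow-up value and compare these differences with a parametric test". It also plans mixed effect models for secondary outcomes and imputation of missing data in general terms. It does not address a test that stopped before isotime.

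**The concern.** The two rules do not fit together. Isotime is chosen so that the two on-treatment tests both reach it, but the analysis then asks for a reading at that time from a third test that had no part in choosing it. If the patient stopped earlier at baseline, no such reading exists and the change cannot be computed.

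The gap is not random. It opens exactly when the patient lasted longer at both Week 10 and EOT than at baseline. Leaving those patients out selects on the baseline-to-treatment gain in endurance. Imputing supplies gas-exchange and symptom values for a moment after the patient had stopped. Using the last value reached at baseline gives up the equal-time comparison that isotime is meant to provide. Each route is liable to bias change-from-baseline isotime results. The direction and size of that bias cannot be derived from the protocol.

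**Working it through.** The plan states no figure for how often isotime values will be available, so there is none to reproduce. The check is whether the two rules can be applied together and, if not, how often they fail.

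**Inputs from the protocol**
- Planned sample size: 26 (synopsis).
- Four tests at the same work rate: baseline (B), Week 10 (W), cross-over (X), EOT (E) (section 2.4.5, Table 1).
- Isotime: T = min(W, E) (section 2.4.5).
- No mean, SD or test-retest figure for ET is given. Everything numerical below therefore rests on assumptions.

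**Step 1. When a value is missing.** The Week 10 change is y_W(T) − y_B(T). The term y_B(T) exists only if B ≥ T, so the baseline value is missing when B < min(W, E). The same holds for cross-over when X < min(W, E).

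**Step 2. Share under exchangeability.** Assume no treatment, learning or period effect, so that all orderings of a patient's times are equally likely.
- Baseline missing: B is the shortest of three (B, W, E), so 1/3; 26 × 1/3 = 8.7, about 9 patients.
- Cross-over missing: likewise 1/3.
- At least one missing: the shortest of four is B or X, so 2/4 = 1/2; 13 patients.
- Both missing: B and X are the two shortest, so (2! × 2!)/4! = 4/24 = 1/6; 4.3, about 4 patients.

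**Step 3. Sensitivity.** Simulation on log ET with assumed inputs: within-patient SD 0.10 to 0.30, nitrite lengthening ET by 0 to 25%, drift of about −5% to +5% per test, and 1:1 sequences.

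| Assumption | Baseline missing | At least one of B, X missing | Both missing |
|---|---|---|---|
| No effect, no drift | 33% | 50% | 17% |
| Effect 10–25%, no drift | 38–49% | 55–66% | 20–32% |
| Effect 0–25%, with drift | 10–74% | 34–80% | 6–43% |

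For baseline alone, out of 26 patients, the rows correspond to about 9, about 10 to 13 (26 × 0.38 = 9.9; 26 × 0.49 = 12.7) and about 3 to 19 (26 × 0.10 = 2.6; 26 × 0.74 = 19.2). The background section cites about 16% longer time to exhaustion with nitrate. At that effect, SD 0.20 and no drift, the baseline share is 42%, about 11 of 26.

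**Step 4. What is not lost.** By construction T ≤ W and T ≤ E, so y_W(T) and y_E(T) both exist for every patient with both tests. With one common baseline, [y_W(T) − y_B(T)] − [y_E(T) − y_B(T)] = y_W(T) − y_E(T), and the baseline cancels. Followed literally, though, the change-score route leaves both brackets undefined when B < T, so a patient whose contrast was fully observed would be dropped or imputed. If X were the period 2 baseline, the second bracket would be y_E(T) − y_X(T) and nothing would cancel.

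**Step 5. After the fix.** With T' = min(B, W, E), T' is no longer than any of the three times, so no completed test lacks a value. Under exchangeability T' is earlier than T in 1/3 of patients, or in 1/2 if X is also included.

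**The case against.** The strongest reply is that section 2.4.5 is a specific rule written for a crossover. It says the endurance test is there to compare nitrite with placebo. Week 10 and EOT are the two on-treatment tests, one per drug, and the shorter of them is the natural isotime for a within-patient contrast. This also mirrors the primary endpoint, which uses no baseline. On that view the baseline sentence in 2.8.1 is generic and should not override the specific rule. The planned mixed models might not need a baseline either, and the CPET laboratory's own procedure description, which the protocol mentions but does not include, may cover tests that stopped early.

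Much of this stands. The direct contrast is complete, and a reader who infers that the nitrite versus placebo comparison at isotime cannot be computed would be wrong.

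A reader might also infer that about half of patients will have no baseline or cross-over value. The documents do not support that. One half is the share missing at least one of the two, and only under exchangeability; the share missing both is 1/6. It also counts the cross-over test as a required pre-treatment value. The protocol does not call that test a period 2 baseline, and its cross-over visit lists supervised dosing and the exercise test, possibly over two days, without giving their order.

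What does not stand is that nothing needs changing. Section 2.8.1 deliberately separates a direct comparison for the primary endpoint from baseline differences for secondary outcomes, and endpoint 7 itself speaks of changes. Two stated rules conflict, and the choice between them decides which patients are analysed.

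**Conclusion.** The concern holds as a conflict between the isotime rule in 2.4.5 and the change-from-baseline analysis in 2.6.2 and 2.8.1. Applied together, they leave no baseline isotime value for about 1/3 of patients (about 9 of 26) if a patient's endurance times are exchangeable. They leave at least one value missing for about 1/2 (13 of 26) only if the cross-over test is also used as a period 2 baseline. Without drift, a nitrite benefit on endurance raises these shares. With drift allowed in either direction, the baseline share could lie anywhere from 10% to 74%. These shares are illustrations of scale and not predictions, because the protocol gives no ET variability.

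The missingness is informative, so change-from-baseline isotime results would be open to bias whether the affected patients are dropped or imputed. The effect is confined to those results. The direct Week 10 versus EOT contrast, endurance time itself and the primary endpoint do not depend on it.

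**What to change.** Make sections 2.4.5, 2.6.2 and 2.8.1 agree before unblinding, in one of two ways.

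1. **Direct contrast.** State that isotime variables are compared within patient, nitrite versus placebo, at the shorter of the Week 10 and EOT times, without change from baseline. This keeps the present isotime rule and uses every patient with both tests. Changes from baseline at isotime would then not be part of the endpoint.
2. **Change from baseline.** If changes are kept, define isotime as the shortest ET of all tests entering the comparison: baseline, Week 10 and EOT, plus cross-over only if it is declared the period 2 baseline. Name the reference test for each period. The downside is an earlier isotime in some patients (1/3 under exchangeability, 1/2 if cross-over is included), where drug differences may be smaller.

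Either option is about a sentence in each section and needs no extra testing.

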## 2.4.6 Laboratory Testing

The following peripheral blood samples will be evaluated at the screening/baseline, week 10, cross-over, and end of treatment visits for follow-up comparison purposes: fasting glucose, comprehensive metabolic panel, hemoglobin A1C, fasting lipid profile, PT/PTT, complete blood count, platelet and differential, NT-proBNP, and research blood samples for plasma

nitrite concentrations, red cell iron-nitrosyl-hemoglobin, and platelet studies. Urine pregnancy test will be performed on females of child-bearing potential at baseline, week 10, cross-over visit, and at the end of study treatment. The samples will be collected and analyzed at the UPMC Presbyterian laboratories. The NT-proBNP blood sample will be sent to the Translational Research Core Laboratory (TRCL) for storage and analysis. Research samples will be sent to [name]/[name] labs in Vascular Medicine Institute (VMI) for storage and analysis.

## 2.4.6.1 Research Laboratory Profiles

Blood samples for platelet mitochondrial analysis, plasma nitrite concentrations and red cell iron-nitrosyl-hemoglobin may be collected at screening/baseline, Week 10, crossover, and EOT visits. These de-identified blood samples will be sent to the [name]/[name] labs in the Vascular Medicine Institute for storage and analysis under the supervision of Drs. [name], [name], and [name].

## 2.4.7 Methemoglobin Levels

The Masimo Rainbow SET® CO-Oximeter device that will be used in this clinical trial has been validated to provide accurate determinations of methemoglobin levels under conditions of hypoxia and methemoglobinemia. Measurements will be obtained before initial dose and approximately 30-45 minutes post initial dose and approximately 30-45 minutes after the dose is given at the clinical visits. Due to unknown reasons the co-oximeter device may not be able to read metHb levels. In that event, a blood sample will be collected to test metHb levels.

## 2.4.8 Right Heart Catheterization, Simultaneous Pressure and Doppler Flow Velocity Measurement, and Exercise RHC

Right heart catheterization (RHC) is performed routinely as a clinical standard of care procedure for diagnostic purposes in this disease population. The standard right heart catheterization is performed with a balloon tipped, flow-directed pulmonary artery catheter (Swan-Ganz catheter), inserted through a sheath in the internal jugular vein. As per standard clinical protocol, hemodynamic recordings of right atrial, right ventricular, pulmonary artery pressures, pulmonary capillary wedge pressure, in addition to cardiac output, are made at baseline.

RHC may be completed at screening for eligibility purposes, week 10, and end of treatment visits. Resting and supine constant workrate exercise RHC measurements will be performed at week 10 and end of treatment. Hemodynamic measurements may be obtained every 2 minutes during the exercise test.

Subjects may also undergo additional hemodynamic measurements using a micromanometer pressure catheter that may be inserted via the Swann-Ganz catheter distal port. Measurements with micromanometer and/or Swann-Ganz catheter may be made with simultaneous flow velocity from transthoracic echocardiographic doppler ultrasound at resting and after the exercise portion of RHC. This portion of the study that involves the micromanometer instrumentation is expected to add an additional 5-10 minutes onto the procedure at each time point.

Cardiac output (CO) is the amount of blood pumped through the left ventricle of the heart in a time interval of one minute. There are a number of ways to calculate CO. Thermodilution and/or Fick cardiac index are two means that will be used for measuring CO for this protocol. The CO will be the average of the recorded CO collected.

Cardiac index (CI) is a measurement that relates the CO from the left ventricle to body surface area (BSA), therefore determining cardiac function to size of the individual. CI is calculated by CO/BSA.

Pulmonary capillary wedge pressure (PCWP) provides an indirect estimate of left atrial pressure (LAP). PCWP is measured by the balloon-tipped, multi-lumen catheter (Swan-Ganz catheter) while it is in a branch of the pulmonary artery. Just behind the tip of the catheter is a small balloon that can be inflated with air (~1 cc). The catheter has one opening (port) at the tip (distal to the balloon) and a second port several centimeters proximal to the balloon. These ports are connected to pressure transducers. When properly positioned in a branch of the pulmonary artery, the distal port measures pulmonary artery pressure and the proximal port measures right atrial pressure. The balloon is then inflated, which occludes the branch of the pulmonary artery. When this occurs, the pressure in the distal port rapidly falls, and after several seconds, reaches a stable lower value that is very similar to left atrial pressure (normally about 8-10 mmHq). The balloon is then deflated and pulmonary artery pressure can again be recorded. The same catheter can be used to measure cardiac output. Anticoagulants would need to be held prior to the right heart catheterization as this is standard clinically for that procedure. Antiplatelets and beta blockers are continued, also clinical standard of care. We will be holding only the morning dose of oral hypoglycemics for all non-insulin dependent diabetics until they complete the study later that morning - this is also standard clinically for this procedure. Holding diuretics along with potassium may also occur as this is often done prior to RHC but will be addressed on a case by case basis by study investigators.

## 2.4.9 Intravenous Glucose Tolerance Test (IVGTT)

This visit will take place in the Montefiore CTRC. This test will occur at least 48 hours after the last exercise bout to account for the effects of acute exercise on insulin resistance. Subjects will be asked not to drink or eat anything other than plain water for 8 hours prior to their arrival for this visit.

Both glucose and insulin will be injected intravenously into the arm. Blood samples will be taken over the course of 3.5 hours, totaling about 15 1/2 tablespoons.

The IVGTT is considered a gold-standard test to measure insulin secretion and sensitivity. It has been standardized and used worldwide for more than 20 years. In our study, the expected duration is 180 mins after the test is started with an IV glucose bolus of 0.3g/kg. After the glucose bolus, a small dose of human regular insulin is given IV to moderate the plasma glucose rise. The insulin dose is 25 mUnits/Kg body weight. Patients taking oral hypoglycemics may be asked to hold those medications the morning of the IVGTT but can resume taking them following the completion of the IVGTT the same day.

